#### **4.4 Study Safety Assessments**

##### **4.4.1 Incidence and Severity of Adverse Events:**

Following the first laser treatment, adverse effects (AEs) will be assessed post-treatment and at each subsequent visit using the following scale:

- 1= mild: requires minimal or no treatment and does not interfere with the subject's daily activities.
- 2= moderate: may cause some interference with functioning.
- 3= severe: interrupts subject's usual daily activity and may require treatment.

#### 4.4.2 Treatment-related Discomfort

After each laser treatment, subjects will be asked to rate the average amount of discomfort experienced during treatment and immediately after laser treatment.

#### 4.4.3 [REDACTED]

#### 4.5 Photographs

Standardized digital photographs will be taken of each subject's treatment area at baseline, prior to and post all laser treatments and at each follow-up visit. Treatment area will be cleansed and any jewelry and make-up will be removed from the area being photographed. For facial photographs, hair will be pulled away from the face with a headband.

Facial photographs will be obtained from at least 3 angles: with the subject facing forward, 45° to the right and 45° to the left. Photographs will be taken in the same windowless room equipped with adequate lighting. The room lighting, camera positioning and subject positioning should be consistent for all study visit photographs. Digital camera settings should remain the same for all photographs and the highest resolution settings should be utilized.

#### 4.6 Study Discontinuation

Cutera, Inc. (the sponsor) has the right to terminate this study at any time. Reasons for terminating the study may include, but are not limited to, the following: incidence or severity of adverse events in this or other studies indicates a potential health hazard to subjects; subject enrollment is unsatisfactory; number of protocol deviations is unacceptable; data recording is inaccurate or incomplete; or questionable study site compliance with ICH-E6, Good Clinical Practice.

#### 4.7 Investigator Selection

The Investigator(s) will be invited to participate in the study based on his or her medical specialty, experience conducting clinical research studies and experience in the use of light-based devices for aesthetic indications. Access to potential study subjects and the Investigator's sincere interest in this study along with expressed willingness to cooperate with the study process and requirements was also considered.

### 5. STUDY POPULATION

#### 5.1 Study Subject Recruitment and Selection

Approximately 60 male or female subjects, ages 18 to 65, with Fitzpatrick Skin Type I-VI who desire laser treatment for rhytides, lentigines, pigmentation, pore size, acne scars, erythema, telangiectasia and skin texture. Subjects will be recruited to participate from the local population. Subjects may also be recruited from the Investigator's existing patient database or from patients who present themselves to the study site requesting treatment. Only subjects who meet all eligibility criteria and who provide written informed consent will be enrolled into the study.

Each subject will be evaluated by the Investigator to assess his/her suitability for entry into the study according to the following inclusion and exclusion criteria.

**5.1.1 Inclusion Criteria**

To be included in the study, subjects must meet all of the following Inclusion Criteria:

1.	Subject must be able to read, understand and sign the Informed Consent Form.
2.	Female or Male, 18 to 65 years of age (inclusive).
3.	Fitzpatrick Skin Type I – VI.
4.	Must be willing to have Cutera excel V laser treatments and able to adhere to the treatments, follow-up visit schedule, and post-treatment care instructions.
5.	Willing to have very limited sun exposure and use sunscreen on the treatment area every day for the duration of the study, including the follow-up period.
6.	Willing to have digital photographs taken of the treatment area and agree to use of photographs for presentation (educational and/or marketing), publications, and any additional marketing purposes.
7.	Agree to not undergo any other cosmetic procedure(s) or treatment(s) on the face during the study and has no intention of having such procedures performed during the course of the study.
8.	For female subjects: not pregnant or lactating and is either post-menopausal, surgically sterilized, or using a medically acceptable form of birth control at least 3 months prior to enrollment and during the entire course of the study.,

**5.1.2 Exclusion Criteria**

Subjects will be excluded from the study if they meet any of the following Exclusion Criteria:

1.	Participation in a clinical trial of another drug, or device administered to the treatment area, within 3 months prior to enrollment or during the study.
2.	Any type of prior cosmetic treatment to the target area within 6 months of study participation, such as laser procedures, facial fillers, toxins and those used for general aesthetic correction.
3.	Use of prescription topicals in the treatment area within one month prior to treatment or use of topical agents one week prior to treatment that may cause facial sensitivity.
4.	Suffering from significant skin conditions in the treated areas or inflammatory skin conditions, including but not limited to, open lacerations or abrasions, hidradenitis, rash, infection , or dermatitis of the treatment area prior to treatment (duration of resolution as per the Investigator’s discretion).
5.	Pregnant and/or breastfeeding, or planning to become pregnant.
6.	Significant concurrent illness, such as diabetes mellitus, immunosuppression/immune deficiency disorders (including HIV infection or AIDS) or using immunosuppressive medication.
7.	Hypersensitivity to light exposure.
8.	Any use of medication that is known to increase sensitivity to light according to the Investigator’s discretion.

9.	History of keloid scarring, hypertrophic scarring or abnormal wound healing or prone to bruising.
10.	Has a history of squamous cell carcinoma or melanoma in the treatment area.
11.	History of epidermal or dermal disorders (particularly if involving collagen or microvasculature), including collagen vascular disease or vasculitic disorders.
12.	A history or active skin condition that in the opinion of the Investigator may interfere/confound with the treatment.
13.	History of connective tissue disease, such as systemic lupus erythematosus or scleroderma.
14.	History of disease stimulated by heat, such as recurrent herpes simplex and/or herpes zoster (shingles) in the treatment area, unless treatment is conducted following a prophylactic regimen.
15.	History of pigmentary disorders, particularly tendency for hyper- or hypo-pigmentation, or any that are considered not acceptable by the study investigator.
16.	Has used oral isotretinoin (Accutane or therapeutic vitamin A supplements of $\geq$ 10,000 units per day) within 12 months of initial treatment or plans on using during the course of the study (note: skin must regain its normal degree of moisture prior to treatment, e.g. lack of noticeable skin flaking and peeling).
17.	Excessively tanned or active sun tan in facial area to be treated, or unable/unlikely to refrain from tanning during the study.
19.	Excessive facial hair in the area to be treated (beards, sideburns, and/or moustache,) that would interfere with diagnosis, assessment, and treatment.
20.	As per the Investigator's discretion, any physical or mental condition which might make it unsafe for the subject to participate in this study, including excessive alcohol or drug abuses, or a condition that would compromise the subject's ability to comply with the study requirements.

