## **1. BACKGROUND INFORMATION**

Non-invasive treatment options are in high demand by patients wanting to improve their appearance without surgical intervention. As a result, patients now have a variety of options for non-invasive skin rejuvenation, from laser and light-based treatments to devices that utilize ultrasound and radiofrequency, however this was not always the case. Initial skin rejuvenation procedures utilized ablative lasers, such as the carbon dioxide (CO2) and erbium:yttrium-aluminum-garnet (Er:YAG), and resulted in substantial improvement in skin appearance, texture, rhytides and laxity[1-3]. However, since ablative treatments destroy the epidermal layer of the skin in order to penetrate and heat the deeper dermal layers, ample post-procedure recovery time is required and patients may experience side effects lasting for a few weeks. Furthermore, hypo- or hyperpigmentation, prolonged wound healing and even scarring can occur following ablative procedures [4-6]. Treatment methods with less risk of side effects and post-treatment down time are in high demand. As such, the choices are vast and varied, ranging from fractional non-ablative laser devices to those that use radiofrequency [7-15]. Fractional lasers inflict microscopic zones of thermal damage in the dermal layers of the skin without destruction of the epidermis, thereby reducing recovery time significantly as compared to ablative procedures[16]. Treatment with non-fractional, non-ablative laser devices requires little to no post-procedure recovery time. Nonablative lasers of various wavelengths are effective for skin rejuvenation based on the principle of selective photothermolysis, whereby laser light is absorbed by hemoglobin in blood vessels and melanin in pigment-producing skin cells [17, 18]. Absorption of laser light by these molecular chromophores results in the production of heat, leading to destruction of unwanted blood vessels and pigment cells. Heat production within the dermis by the laser light also results in immediate collagen contraction and heat-induced wound healing that, over time, causes a cascade of cellular events leading to new collagen production and improved skin appearance [8, 10, 19-23].

[REDACTED]

[REDACTED]

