### **4. STUDY DESIGN**

This is an open-label, prospective, study in approximately 60 male or female subjects, age 18 to 65 years who desire laser treatment for the improvement of rhytides, lentigines, pigmentation, erythema, telangiectasia, pore size and skin texture. [REDACTED]

[REDACTED]. Subjects will receive [REDACTED] laser treatments, [REDACTED]. Subjects will be contacted by phone 7 days [REDACTED] after their first treatment for follow-up. Subjects will return to the site after final study treatment for two follow-up visits: 6 and 12 weeks [REDACTED]).

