## 5.2 Subject Numbering

If a subject completes the Informed Consent Form, meets the study eligibility criteria and is willing to participate, the subject will be assigned a study subject identification number. This number is comprised of a site number (which is provided by the sponsor) and a sequential subject number and the subject initials (first and last names).

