### **12.3 Protocol Compliance**

The principal investigator must comply with all terms of the protocol.

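### Does exclusion 15, on pigmentary disorders, shut out the subjects whom the study recruits for pigmentation?

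*Combined protocol and SAP*

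**What the plan says.** The target conditions appear in two descriptive sentences. Section 4 speaks of subjects "who desire laser treatment for the improvement of rhytides, lentigines, pigmentation, erythema, telangiectasia, pore size and skin texture". Section 5.1 speaks of subjects "who desire laser treatment for rhytides, lentigines, pigmentation, pore size, acne scars, erythema, telangiectasia and skin texture". The background in Section 1 explains that light absorbed by blood and pigment produces heat, "leading to destruction of unwanted blood vessels and pigment cells".

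Exclusion 15 in Section 5.1.2 then bars "History of pigmentary disorders, particularly tendency for hyper- or hypo-pigmentation, or any that are considered not acceptable by the study investigator". Meeting any one exclusion keeps a subject out. Section 5.1 adds: "Only subjects who meet all eligibility criteria and who provide written informed consent will be enrolled into the study". Section 12.3 adds: "The principal investigator must comply with all terms of the protocol". Exclusion 14, on heat-triggered disease, does carry an exception: "unless treatment is conducted following a prophylactic regimen". Exclusion 15 carries none.

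**The concern.** Pigment is both a treatment target and the subject of an exclusion, and no sentence separates the subject who is wanted from the subject who is barred. The closing clause on the investigator's view does not clearly help. It is joined by *or*, so grammatically it adds disorders to the exclusion and does not permit exceptions.

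If the broad reading were applied, a study that Section 3 calls pivotal could end with no adverse event data on people treated for pigmentation. If the narrow reading were applied, a strict auditor might record those same people as enrolled in breach of a criterion. With several sites, the same person might be classified differently from one to another.

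Two smaller points add to the impression of a loosely defined population: the target lists in Sections 4 and 5.1 differ, and none of the visible inclusion criteria requires a target condition to be present.

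**Working it through.** The plan gives no figure to reproduce, so the check is mainly a comparison of texts.

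**1. Target lists.**
- Section 4: rhytides, lentigines, pigmentation, erythema, telangiectasia, pore size, skin texture = 7.
- Section 5.1: the same 7 plus acne scars = 8.
- Difference: 8 − 7 = 1 item. Neither sentence is an eligibility criterion.

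**2. What exclusion 15 touches.** Pigmentation is clearly within reach of a broad reading: 1 of 8 targets. Lentigines would make it 2 of 8 only if they count as a pigmentary disorder, and no visible text says so.

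**3. Which reading the text supports.**
- The criterion stresses a tendency, which describes predisposition and not a lesion already present.
- Its neighbours concern how skin may react to treatment: scarring, poor healing and easy bruising (exclusion 9), disease set off by heat (14) and a current tan (17).
- Section 1 itself mentions pigment change as a complication, although of ablative procedures.
- Section 5.1 names pigmentation as a reason for recruitment just before the criteria begin. A reading under which the criteria cancel that sentence is the less natural one.
- The broad method proves too much. Exclusion 11 bars a history of epidermal or dermal disorders, with emphasis on collagen and small vessels. Read the same way, it would threaten telangiectasia, erythema and much of the rest of the list.

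**4. Entry condition.** Inclusion criteria that require a target condition: 0 of 8. Visible exclusions that bar a subject for lacking one: 0 of 19 (numbers 1 to 17, 19 and 20). However, Section 6.1 on screening is listed in the contents and its text is blacked out. Text after the target list in Section 4 and part of Section 4.3.1 is also blacked out, and exclusion 18 is not visible. Absence from the visible text therefore does not show absence from the plan.

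**5. Effect on the endpoints.** The safety endpoint in Section 4.1.1 counts device-related adverse events and grades them, without division by target condition. The efficacy endpoint in Section 4.1.2 is the investigator's rating of skin quality. Both are defined whoever is enrolled.

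One could try to size the loss with the exact one-sided 95% upper limit for zero events in n subjects, 1 − 0.05^(1/n):

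| Assumed n | Upper limit |
|---|---|
| 15 | 18.1% |
| 30 | 9.5% |
| 60 | 4.9% |

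Only 60 comes from the plan, as the approximate total enrolment. The plan does not say how many subjects would have pigmentation as a target. The limits hold for any group of the stated size, and no visible text plans an analysis by target condition. They do not measure an effect of exclusion 15.

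**The case for a change.** The best case for a change is that eligibility criteria ought to be clear on their face. The list shows that its authors could write an exception (14) and could leave a whole criterion to the investigator's judgement (12 and 20). Exclusion 15 does neither in plain terms. Since any single exclusion bars entry, the unseen exclusion 18 would be unlikely to lift it. Clarification would take a sentence, with no added visit or subject.

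Part of this stands: there is no stated exception, the narrow reading is not spelled out, and a sponsor revising the document for other reasons might tidy it. The rest does not carry the point to a change.

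- The request would be to write down how the criterion applies, without saying which way. The clinical choice belongs to the sponsor. In practice the investigator, who under Section 5.1 judges each subject's suitability against the criteria, would settle it sensibly.
- The between-site argument lacks a shown basis. Section 5.2 builds the subject number from a site number, which allows for several sites but does not establish them, and much of the visible text is written in the singular.
- Low cost alone does not justify an amendment when no effect on an endpoint has been shown.

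**Conclusion.** No change to the plan is called for. Exclusion 15 is loosely worded against the recruitment sentence, but its emphasis and its setting point to a safety screen that can coexist with recruiting for pigmentation. An experienced investigator can be expected to fill that gap. The size is at most 1 of 8 targets clearly affected, with no shown effect on the safety or efficacy results. The 7-against-8 list difference is a clerical slip in descriptive text. The question of a required target condition cannot be decided from the visible pages.

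This rests on two assumptions: that investigators read exclusion 15 in its more natural sense, and that the blacked-out screening and design text does not impose the broad one. If investigators did apply the broad reading, the pooled safety result would still be valid for the people enrolled, but it would not describe subjects treated for pigmentation.

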## 5.2 Subject Numbering

If a subject completes the Informed Consent Form, meets the study eligibility criteria and is willing to participate, the subject will be assigned a study subject identification number. This number is comprised of a site number (which is provided by the sponsor) and a sequential subject number and the subject initials (first and last names).

## 5.3 Subject Discontinuation Criteria

If possible, every subject should remain in the study until completion of the required follow-up period. However, participation in this study is completely voluntary and a subject can choose to withdraw from the study at any time. Decision to withdraw will not affect or prejudice the subject's continued medical care in any way. In those instances, the investigator will attempt to obtain a final clinical assessment and an adverse device effect evaluation for the subject prior to this withdrawal. A subject will be considered lost to follow-up only after three unsuccessful, documented attempts to contact the subject have been made.

In addition, a subject can be discontinued for any of the following reasons: the Principal Investigator decides that continuing in the study would not be in the subject's best interest, a subject is noncompliant

[REDACTED]

[REDACTED]

[REDACTED]

[REDACTED]

[REDACTED]

[REDACTED]

[REDACTED]

[REDACTED]

[REDACTED]

[REDACTED]

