#### **4.1 Study Endpoints**

##### **4.1.1 [REDACTED] Safety Endpoint**

Safety of the Cutera excel V laser and the Micro-Lens Array attachment assessed by the frequency and severity of device related adverse events.

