#### **4.2 Study Duration**

Subjects enrolled in this trial will participate for approximately 14 months, [REDACTED], [REDACTED], and 2 follow-up visits at 6 and 12 weeks [REDACTED] post final treatment. In

total, enrolled subjects will complete up to 9 visits: 1 screening visit, 1 week phone follow-up after first treatment, up to [redacted] laser treatment visits, and 2 required follow-up visits.

The screening and first laser treatment may be combined into one visit provided that the subject has signed the IRB-approved Informed Consent Form prior to the commencement of any study-related procedures and has met all criteria to be enrolled in the study.

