**7.3 Follow-up of subjects after AEs/ADEs and SAEs/SADEs:**

All reported AEs/ADEs/SAEs/SADEs should be followed until resolution or until the subject’s participation in the study ends. Resolutions of AEs/ADEs/SAEs/SADEs are to be documented on the appropriate CRFs. All ADEs that result in permanent discontinuation from this clinical trial, whether serious or not, should also be reported on the subject Non-Completion of Study Form.

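### Unless redacted text provides otherwise, Sections 5.3 and 7.3 let follow-up of a device effect end when that effect ends the subject's participation

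*Combined protocol and SAP*

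**What the plan says.** The study is an "open-label, prospective, study in approximately 60 male or female subjects". Under 4.1.1, safety is "assessed by the frequency and severity of device related adverse events". Section 4 says "Subjects will return to the site after final study treatment for two follow-up visits: 6 and 12 weeks", and 4.2 calls them "2 required follow-up visits".

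Section 5.3 opens with an expectation that, where possible, everyone stays through the required follow-up. It then describes voluntary withdrawal and says that in such cases "the investigator will attempt to obtain a final clinical assessment and an adverse device effect evaluation for the subject prior to this withdrawal". A new paragraph adds that "a subject can be discontinued for any of the following reasons: the Principal Investigator decides that continuing in the study would not be" (the sentence then names the best interest of the subject). It goes on to noncompliance and breaks off there into redaction, which continues to Section 7.

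Section 7.2 requires events to be sought at each contact and recorded with, among other items, severity, resolution date and outcome. Section 7.3 has reported events followed to resolution or to the end of the subject's participation. It also says "All ADEs that result in permanent discontinuation from this clinical trial, whether serious or not" go on the Non-Completion of Study Form as well.

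**The concern.** In the legible text, the only form of early stopping is leaving the study. Nothing legible describes a subject who stops laser treatment but stays in follow-up. Section 7.3, which shows no redaction, expects device effects that end participation and also allows event follow-up to end with participation. Read together, the two rules can cut observation short in the subjects whose device effects were bad enough to take them out.

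Safety rests on the severity of device-related events as well as their number. An event graded at exit may worsen, persist or resolve, and a new effect may appear later. If the subjects in whom this is most likely are not seen again, late safety is described mainly from subjects who did better. The legible text shows no comparator arm that would reveal the imbalance.

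**Working it through.** **1. Trace one case through the legible rules.** A subject has a device effect during the treatment course, and the investigator ends participation.

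- *The triggering event:* captured. It is graded under 4.4.1, recorded under 7.2 and reported again under 7.3.
- *Exit evaluation:* 5.3 attaches the attempt to voluntary withdrawal. The investigator-led route has none in the part that can be read.
- *Course after exit:* 7.2 asks for a resolution date and an outcome, but 7.3 lets follow-up stop when participation ends, so both can be left open.
- *New effect after exit:* no legible contact is scheduled at which it would be found.
- *The 6- and 12-week visits:* 5.3 states the general expectation to stay, but no legible procedure applies it to a discontinued subject.

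**2. Could the visits still be held?** Yes. Both are timed from the final treatment, so they can be counted from the last treatment received.

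**3. Is there a figure in the plan to reproduce?** No. The contents list names Sections 10.1 (sample size) and 10.2 (analysis methods), but neither is legible. The arithmetic below is for scale only. The 60 comes from Section 4; every other input is an assumption.

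*Loss of numbers alone.* With no late event among n subjects followed, the one-sided 95% upper bound is 1 − 0.05^(1/n). For n = 60, 57, 54 and 48 it is 4.9%, 5.1%, 5.4% and 6.1%. Losing a few subjects at random costs little.

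*Selective loss.* Let d subjects leave, with an effect present at 12 weeks in a proportion q of leavers and p of the rest. The true proportion is [(60 − d)p + dq]/60. Among attenders it is p, so the difference is d(q − p)/60.

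- d = 6, p = 2%, q = 10%: (1.08 + 0.6)/60 = 2.8%, against 2.0% among attenders.
- d = 6, p = 2%, q = 30%: (1.08 + 1.8)/60 = 4.8%, against 2.0%.
- d = 6, p = 2%, q = 50%: (1.08 + 3.0)/60 = 6.8%, against 2.0%.
- p = 5%, q = 50%, d = 3, 6, 12: 4.35/60 = 7.25%, 5.7/60 = 9.5% and 8.4/60 = 14.0%, against 5.0% each time.

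The chance that at least one leaver has an effect at 12 weeks that nobody sees is 1 − (1 − q)^d. For d = 6 and q = 10%, 30%, 50% it is 47%, 88% and 98%.

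**4. What this shows.** The difference is zero when q = p and grows with d and with q − p. It concerns the proportion with an effect present at 12 weeks, which is not the endpoint in 4.1.1. A leaver whose triggering event was recorded already counts towards frequency. The arithmetic therefore gives a direction and a sensitivity, and does not estimate bias in the safety endpoint.

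**The case against.** The strongest objection is redaction. Section 5.3 stops mid-sentence, and Section 6 (whose 6.4 covers phone and follow-up visits) and the study schedule in Appendix 1 cannot be read. A rule for discontinued subjects would normally sit in one of these places, and redacted text may not be treated as absent. This stands, and it makes the point conditional.

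The legible text also leans partly the other way. Section 5.3 asks that every subject stay through follow-up if possible. Section 4.2 sets the number of treatments as a maximum and calls the follow-up visits required, which fits a shortened course followed by both visits. This shows intent, but it supplies no procedure for a subject the investigator discontinues, and it does not alter the end point for event follow-up in 7.3.

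Three stronger readings are tempting, and the documents support none of them:

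- *A reader might infer that only voluntary leavers get an exit evaluation.* The visible wording is tied to them, but the investigator-led paragraph is incomplete.
- *A reader might infer that late device effects are missed in subjects removed for harm.* The event causing the exit is recorded. Only its later course, or a new effect, is exposed, and it can be missed rather than must be. Removal for harm is not a named reason in the legible part of 5.3, although 7.3 does foresee it.
- *A reader might take the 2.25 to 9.0 percentage-point differences in the 5%/50% illustration as the size of the bias.* They follow from assumed rates and concern 12-week prevalence, which is not the stated endpoint.

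Finally, subjects who withdraw consent cannot be required to return, and some discontinued subjects will not want to. This is correct and limits what any change can recover.

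**Conclusion.** The point holds in a limited and conditional form. Following 7.3 as written can end observation of an unresolved device effect when the subject is discontinued because of it, and the legible part of 5.3 neither extends the exit evaluation to that subject nor keeps the subject on the 6- and 12-week visits. The consequence is possible understatement of the severity, duration and late occurrence of device-related events. The count of events that trigger an exit is not affected.

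The documents do not allow the amount to be estimated. The direction favours the device if discontinued subjects have more late or persistent effects than the rest, which is plausible but assumed. The conclusion also assumes that neither the hidden part of 5.3 nor Section 6 already keeps these subjects in follow-up; if either does, the point falls. The change is cheap and worth making, but the point is not evidence of a demonstrated bias.

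**What to change.** First, check whether the redacted part of 5.3 or Section 6 already keeps discontinued subjects in safety follow-up through both visits. If it does, a cross-reference from 7.3 is enough. If it does not:

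- In 5.3, distinguish stopping laser treatment from leaving the study. Ask subjects who stop treatment for any reason other than withdrawal of consent to attend the 6- and 12-week visits, counted from the last treatment received.
- In 5.3, apply the attempted exit evaluation to every early exit, whoever initiates it.
- In 7.3, follow unresolved device-related events through the 12-week visit unless consent is withdrawn, which brings it into line with the outcome and resolution date required by 7.2. Record device effects that stop treatment separately from those that end participation.

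The criteria for stopping treatment are unchanged. The cost is protocol wording, one extra field on the Non-Completion of Study Form, and two already-scheduled visits for a few subjects, some of whom will decline.
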